Investigator-Initiated Trial Study Protocol

Safety and Efficacy of an Intracanalicular Dexamethasone Insert compared to Topical Loteprednol Etabonate Ophthalmic gel 0.38% in Patients with Keratoconus (KC) wearing Rigid Gas Permeable (RGP) Contact Lenses who have been diagnosed with Allergic Conjunctivitis and underlying Dry Eye Disease (DED)

The [name] Study

Compound: DEXTENZA (dexamethasone ophthalmic insert) 0.4 mg, for intracanalicular use

Study Name: The [name] STUDY

Clinical Phase: Open-label, Prospective, Interventional

Date of Issue: February 20, 2020

Primary Investigator: [name], OD
[contact]

Research Coordinator: [name]
Senior Research Coordinator

Site Name & Location: Cornea Center for Clinical Excellence
Illinois College of Optometry
Illinois Eye Institute
[contact]

CLINICAL STUDY PROTOCOL SYNOPSIS

TITLE	Safety and Efficacy of an Intracanalicular Dexamethasone Insert compared to Topical Loteprednol Etabonate Ophthalmic gel 0.38% in Patients with Keratoconus (KC) wearing Rigid Gas Permeable (RGP) Contact Lenses who have been diagnosed with Allergic Conjunctivitis and underlying Dry Eye Disease (DED)- The [name] Study
SITE LOCATION(S)	Cornea Center for Clinical Excellence Illinois College of Optometry Illinois Eye Institute [contact]
PRINCIPAL INVESTIGATOR	[name], OD [contact]
OBJECTIVE(S)	To determine if physician administered intracanalicular dexamethasone insert improve the signs and symptoms of ocular allergy and dry eye disease in KC patients compared to topical loteprednol etabonate ophthalmic gel 0.38%.
STUDY DESIGN	Prospective Open-label Interventional Study
STUDY DURATION	4 months after IRB approval
ESTIMATED STUDY COMPLETION DATE	3 months after DEXTENZA insertion
POPULATION	
Sample Size:	20 patients (40 eyes)
Target Population:	Patients with bilateral keratoconus, wearing RGP contact lenses in both eyes, who have been diagnosed with bilateral allergic conjunctivitis and underlying dry eye disease
TREATMENT(S)	
Study Drug	DEXTENZA (dexamethasone ophthalmic insert) 0.4 mg, for intracanalicular use
Dose/Route/Schedule:	Patients with Keratoconus, with Allergic Conjunctivitis and underlying Dry Eye Disease, wearing RGP contact lenses will have one eye randomized to receive the Sustained Release Dexamethasone, 0.4mg intracanalicular insert (study eye). The fellow-eye will receive topical loteprednol (control eye) on a 4,3,2,1 weekly taper schedule.
ENDPOINT(S)	

Primary:

To determine the effect of dexamethasone intracanalicular insert through Day 90 as measured by:

- Mean change in itching score from Baseline measured at all visits (Visits 1-5)
 - Graded on a scale of 0-4 and determined by asking the patient
- Mean change in palpebral conjunctivitis papillae score from Baseline measured at all visits (Visits 1-5)
 - Graded using the Papillae Efron Scale as graded by the physician
- Mean change in conjunctival injection score from Baseline measured at all visits (Visits 1-5)
 - Graded on a scale of 0-4 as graded by the physician
- Mean change in corneal staining score from Baseline measured at all visits (Visits 1-5)
 - Graded using the NEI Fluorescein Staining Scale as graded by the physician

Secondary:

To determine the effect of dexamethasone, insert through Day 90 as measured by:

- Physician ease of insertion as measured by a 0-10-point scale
- Vision-related Quality of Life (QOL) assessment as measured with OSDI Questionnaire measured at all visits (Visits 1-5)
- Uncorrected and corrected VA mean change from Baseline measured at all visits (Visits 1-5)
- Patient's therapy of preference as measured by the Comparison of Ophthalmic Medications for Tolerability Questionnaire (COMTOL) at final visit (Visit 5)
- Mean change in MMP9/osmolarity from Baseline measured at all visits (Visits 1-5)
- Incidence of IOP spikes (IOP increased \geq 10mmHg from baseline)

TABLE OF CONTENTS

Clinical Study Protocol Synopsis 2

List of Tables 5

1. Introduction and Rationale 6

1.1 Introduction 6

1.2 Rationale..... 6

1.2.1 Rationale for Study Design 7

2. Study Objectives 7

2.1 Primary Objective..... 7

2.2 Secondary Objectives 7

3. Study Design..... 8

3.1 Study Description and Duration 8

4. Selection, Withdrawal, and Replacement of Patients 8

4.1 Study Population 8

4.1.1 Inclusion Criteria..... 8

4.1.2 Exclusion Criteria..... 8

4.2 Treatment Logistics and Accountability 9

4.2.1 Packaging, Labeling, and Storage 9

4.2.2 Supply and Disposition of Treatments 9

4.2.3 Treatment Accountability..... 9

4.3 Concomitant Medications and Procedures 10

5. Study Schedule of Events and Visit Descriptions 10

5.1 Schedule of Events 10

5.2 Study Visit Descriptions 12

5.2.1 Study Procedures..... 12

5.2.2 Unscheduled Visits..... 14

5.2.3 Adverse Event Information Collection..... 14

5.3 Rescue Criteria..... 14

6. Safety Definitions, Reporting, and Monitoring..... 14

6.1 Definitions 14

6.1.1 Adverse Event 14

1. INTRODUCTION AND RATIONALE

1.1 Introduction

Keratoconus is a bilateral, asymmetric, non-inflammatory corneal ectasia characterized by progressive thinning of the corneal stroma resulting in corneal bulging and distortion.ⁱⁱⁱ Such pathological changes to the cornea not only cause decreased visual acuity, but also have been associated with reduced tear film qualityⁱⁱⁱ and overall ocular discomfort.^{iv} A recent study demonstrated that keratoconic patients have a greater incidence of dry eye pathology – specifically, greater tear instability and corneal staining as well as decreased tear volumes.^v There is emerging evidence demonstrating that the predominance of dry eye is evaporative in nature^{vi}—the major cause being meibomian gland dysfunction (MGD).^{vii} Eye rubbing, family history of keratoconus, allergy, asthma, and eczema have been demonstrated to be important risk factors according to the most recent systematic review and meta-analysis.^v

Ocular allergy can alter the dry eye disease cycle including tear film instability, ocular surface inflammation and neurosensory abnormalities. The TFOS DEWS II Report has included allergic conjunctivitis among one of the likely risk factors for dry eye disease. Both allergic conjunctivitis and dry eye are associated with inflammation. Inflammation may be present before the clinical signs of dry eye, contributing to increased corneal desquamation and corneal surface irregularity.

Steroids play an important role in the treatment of both allergic conjunctivitis and dry eye disease. The anti-inflammatory properties of dexamethasone and other synthetic glucocorticoids can benefit the status of dry eye and allergic conjunctivitis via modification of a wide variety of immune functions.^{viii} The immune-modifying properties of dexamethasone can improve dry eye and allergy status not only by inhibiting the inflammation that has already occurred as a result of the initiated immunological priming, but also by potentially preventing initiating immune responses from recurring.

1.2 Rationale

Drug delivery platforms are an innovative exciting advancement in ophthalmology. They allow patients to eliminate topical medications which are generally associated with lack of compliance, difficulty of use and requiring help from family members. These delivery systems can be applied easily in office, and patients do not have to worry about drop insertion in their post-operative regimen.

The results of this research project should help to answer the following question: Does the use of a physician administered intracanalicular dexamethasone insert improve the signs and symptoms of ocular allergy and dry eye disease in KC patients compared to the use of topical loteprednol etabonate ophthalmic gel 0.38%?

1.2.1 Rationale for Study Design

This prospective study will use a fellow-eye design for 20 participants (40 eyes) with bilateral keratoconus, wearing RGP contact lenses in both eyes, who have been diagnosed with bilateral allergic conjunctivitis and underlying dry eye disease. Per participant, one eye will be randomized to receive the intracanalicular dexamethasone insert at the baseline visit (study eye), while the other eye will be assigned to receive the standard of care topical lotemax etabonate ophthalmic gel 0.38% (control eye). Thus, for every eye in the study group, there will be a paired eye with similar baseline characteristics in the control group sourced from the same participant. The fellow-eye design allows for greater control of potential confounders tied to participants' systemic and ocular health.

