2. STUDY OBJECTIVES

2.1 Primary Objective

To determine the effect of dexamethasone intracanalicular insert through Day 90 as measured by:

- Mean change in itching score from Baseline measured at all visits (Visits 1-5)
 - Graded on a scale of 0-4 and determined by asking the patient
- Mean change in palpebral conjunctivitis papillae score from Baseline measured at all visits (Visits 1-5)
 - Graded using the Papillae Efron Scale as graded by the physician
- Mean change in conjunctival injection score from Baseline measured at all visits (Visits 1-5)
 - Graded on a scale of 0-4 as graded by the physician
- Mean change in corneal staining score from Baseline measured at all visits (Visits 1-5)
 - Graded using the NEI Fluorescein Staining Scale as graded by the physician

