3. STUDY DESIGN

3.1 Study Description and Duration

This prospective, open-label, single-center, randomized, fellow-eye, investigator-sponsored clinical study seeks to investigate the safety and efficacy of the dexamethasone insert in the treatment of allergic conjunctivitis and DED signs and symptoms in patients with Keratoconus using RGP contact lenses when compared to topical standard of care loteprednol etabonate ophthalmic gel 0.38%. After screening a given patient for inclusion and exclusion criteria, and gaining informed consent, one eye will be randomized to receive the dexamethasone insert as determined by a coin flip at the screening visit. The remaining eye will be prescribed a loteprednol etabonate ophthalmic gel 0.38% following a 4,3,2,1 weekly taper. Per enrolled eye, the study period will last for approximately 90 days, consisting of five visits. At Screening/ Baseline, Day 0, Day 7, Day 30 and Day 90, primary and secondary endpoints will be assessed alongside standard-of-care procedures. Adjusting for enrollment period, the study will last a total of approximately 3 months. An abstract with preliminary results will be submitted by May 2020 for the AAOpt conference.

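### No baseline adjustment is specified for the four change-from-baseline primary measures, although nothing ensures that fellow eyes start alike; adjusting would usually improve precision at 20 pairs

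*Combined protocol and SAP*

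**What the plan says.** Section 1.2.1 gives the reason for the fellow-eye design: for each treated eye "there will be a paired eye with similar baseline characteristics in the control group". Under section 3.1, "one eye will be randomized to receive the dexamethasone insert as determined by a coin flip at the screening visit". The synopsis sets the sample at 20 patients, hence 20 within-patient pairs.

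Section 2.1 and the synopsis define all four primary measures in the same way. For corneal staining, for example, the measure is "Mean change in corneal staining score from Baseline measured at all visits (Visits 1-5"; itching, papillae and conjunctival injection follow the same pattern.

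Section 4.1.1 requires an Efron papillae score of at least 1 with itching, and an NEI staining score of at least 1, in both eyes. These are lower limits only. The combined document has no statistical analysis section: it names no test, model, paired method, covariate, alpha or power.

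**The concern.** The question in section 1.2 is comparative, insert against loteprednol gel, and it rests on 20 pairs. A patient who barely qualifies in one eye and has much heavier staining in the other is eligible, so the similarity in section 1.2.1 is asserted rather than built in. The coin flip balances the eyes on average, but not in the one sample that will be observed.

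If the endpoint wording is applied as it stands, the natural analysis is the paired difference in raw change. That estimate gives the baseline difference a fixed weight of one, whatever its actual relation to the follow-up difference. Two things follow. The interval is usually wider than it need be. And if the eyes assigned to one treatment happen to start worse, regression to the mean makes that treatment look better. Both can be reduced with data that the schedule of events already collects.

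**Working it through.** The plan gives no figure to reproduce: 20 patients is stated without alpha, power, effect size or SD.

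**Inputs**
- n = 20 pairs (synopsis).
- Allocation within patient by coin flip (3.1), so the expected baseline difference between treatments is zero.
- D0 and D1: insert eye minus control eye, at baseline and at a follow-up visit.
- s: SD of the between-eye difference, assumed equal at both times.
- r: correlation of D0 with D1. It is not in the documents; 0.3, 0.5 and 0.7 are assumed.
- Normal theory, which is approximate because the scales are ordinal.

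**Precision**
- Raw paired change, mean(D1 − D0): variance = 2s²(1 − r)/n.
- Adjusted, the intercept of D1 regressed on D0: variance = s²(1 − r²)/n × (n − 2)/(n − 3). The last factor, 18/17 here, is the price of estimating the slope.
- Ratio, adjusted to raw: (1 + r)/2 × 18/17. Unadjusted pairs giving the same precision: 20/ratio.

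| r | Raw variance (s²) | Adjusted variance (s²) | Ratio | Equivalent unadjusted pairs |
|---|---|---|---|---|
| 0.3 | 1.4/20 = 0.070 | 0.91/20 × 18/17 = 0.048 | 0.69 | 29 |
| 0.5 | 1.0/20 = 0.050 | 0.75/20 × 18/17 = 0.040 | 0.79 | 25 |
| 0.7 | 0.6/20 = 0.030 | 0.51/20 × 18/17 = 0.027 | 0.90 | 22 |

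Break-even is where (1 + r)/2 × 18/17 = 1, so r = 34/18 − 1 = 0.89. At r = 0.9 the ratio is 1.01: adjustment gains nothing and costs about 1%.

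**Conditional error**
- SE of the mean baseline difference: s/√20 = 0.22s. An imbalance of 1.96 SE is 0.44s, which either direction together reaches in 5% of randomizations per endpoint.
- Given a mean baseline difference d, raw change is off by −(1 − r)d. At d = 0.44s the size is 0.31s, 0.22s and 0.13s for r = 0.3, 0.5 and 0.7. At one SE and r = 0.5 it is 0.11s.
- Lower scores are better, so if insert eyes start worse (d > 0) the error favours the insert, and the reverse.
- These are units of the between-eye difference. If the two eyes' scores correlate at 0.8 (assumed), s = √(2 × 0.2) = 0.63 score SD, and 0.22s is about 0.14 score SD.

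**Simulation** (100,000 trials per scenario, two-sided 5% assumed)
- Raw change averaged 0.00 for a true effect of 0 and 0.60 for a true 0.6s. Its type I error was 5.0% at each r.
- Power for a true 0.6s, raw against adjusted: 58% against 74%, 72% against 81%, and 91% against 93% at r = 0.3, 0.5 and 0.7.
- Among trials with an imbalance near 0.44s, type I error of raw change was about 14%, 12% and 10%, against about 5% with adjustment.

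**The case against.** The main counter-argument is that the protocol never prescribes an unadjusted comparison. A reader might infer one from the phrase mean change, but section 2.1 defines a measure, not a test. Nor does the measure exclude adjustment: regressing D1 − D0 on D0 gives the same intercept as regressing D1 on D0. On this view the larger gap is the missing analysis plan, and baseline adjustment is one detail of it. That stands. The detail still has to be settled in advance.

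A reader might also infer that chance imbalance biases the trial's result. It does not, in the usual sense: over coin-flip randomizations paired change is unbiased and holds its error rate. The error is conditional on the imbalance that occurs. Nor is a large imbalance likely in any one endpoint. Beyond 0.44s it is a 5% event, or 1 − 0.95⁴ = 19% for at least one of four if the four were independent.

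Finally, a reader might set section 1.2.1 against section 1.1, which says "Keratoconus is a bilateral, asymmetric, non-inflammatory corneal ectasia", and call it a contradiction. The adjective describes the ectasia. The staining and tear-film findings cited there concern keratoconic patients, not one eye against the other, and section 4.1.1 requires bilateral allergy and dry eye. At most there is indirect tension for corneal staining. Change scores do not depend on similar eyes in any case, since each eye's own baseline is subtracted.

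**Conclusion.** The point holds as a matter of efficiency and of protection against conditional error, not as a flaw that invalidates the comparison. Between-eye similarity at baseline is not assured, and no adjustment is planned. With the assumed r of 0.3 to 0.7, adjustment removes roughly 31% to 10% of the variance. In an unlucky draw (1.96 SE) it avoids an error of 0.31 to 0.13 of the SD of the between-eye difference. The size depends wholly on r, which the documents do not give, and on equal SDs at the two times. For r near 0.9 there is nothing to gain. The change is worth making because precision is scarce at 20 pairs, but it is modest.

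**What to change.** Write the primary analysis as follows. For each primary score and each post-treatment visit, take the within-patient difference (insert minus control), regress it on the within-patient baseline difference, and report the intercept with its 95% CI as the treatment effect. Tabulate baseline scores by treated eye.

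Two points must be settled first:
- **Baseline.** Table 1 records every primary score at both Visit 1 (Day −30 to −1) and Visit 2 (Day 0), and section 1.2.1 places insertion at the baseline visit while Table 1 places it at Visit 2. Name one baseline in advance: the last assessment before either eye is treated.
- **Itching.** Appendix I asks the patient for a current level and does not say per eye. The model applies to papillae, injection and staining as they stand, and to itching only if each eye is scored separately.

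The cost is analysis wording and one degree of freedom. No new measurements are needed for the three physician-graded scores; for itching, the case report form may need an entry for each eye.

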2. STUDY OBJECTIVES

2.1 Primary Objective

To determine the effect of dexamethasone intracanalicular insert through Day 90 as measured by:

- Mean change in itching score from Baseline measured at all visits (Visits 1-5)
 - Graded on a scale of 0-4 and determined by asking the patient
- Mean change in palpebral conjunctivitis papillae score from Baseline measured at all visits (Visits 1-5)
 - Graded using the Papillae Efron Scale as graded by the physician
- Mean change in conjunctival injection score from Baseline measured at all visits (Visits 1-5)
 - Graded on a scale of 0-4 as graded by the physician
- Mean change in corneal staining score from Baseline measured at all visits (Visits 1-5)
 - Graded using the NEI Fluorescein Staining Scale as graded by the physician

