2.2 Secondary Objectives

To determine the effect of dexamethasone, insert through Day 90 as measured by:

- Physician ease of insertion as measured by a 0-10-point scale
- Vision-related Quality of Life (QOL) assessment as measured with OSDI Questionnaire measured at all visits (Visits 1-5)
- Uncorrected and corrected VA mean change from Baseline measured at all visits (Visits 1-5)
- Patient's therapy of preference as measured by the Comparison of Ophthalmic Medications for Tolerability Questionnaire (COMTOL) at final visit (Visit 5)
- Mean change in MMP9/osmolarity from Baseline measured at all visits (Visits 1-5)

- Incidence of IOP spikes (IOP increased \geq 10mmHg from baseline)

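### The aim is insert versus gel, but the primary endpoint is written as the insert's change from Baseline on four unranked scales at all visits, and the between-eye difference is never made the endpoint statistic

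*Combined protocol and SAP*

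**What the plan says.** **The aim is comparative.** The synopsis objective asks whether the insert will "improve the signs and symptoms of ocular allergy and dry eye disease in KC patients compared to topical loteprednol etabonate ophthalmic gel 0.38"%. Section 1.2 puts the same question: does it "improve the signs and symptoms of ocular allergy and dry eye disease in KC patients compared to the use of topical loteprednol etabonate" gel? Section 3.1 describes a randomised fellow-eye study with the gel as comparator. Section 1.2.1 explains the pairing: "for every eye in the study group, there will be a paired eye with similar baseline characteristics in the control group".

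**The primary endpoint is not worded that way.** Section 2.1, repeated in the synopsis, begins "To determine the effect of dexamethasone intracanalicular insert through Day 90 as measured by" and gives four bullets: itching, papillae, conjunctival injection and corneal staining. The first reads "Mean change in itching score from Baseline measured at all visits (Visits 1-5"), and the others follow the same pattern. The gel and the control eye are not mentioned, the scales are not ranked and no visit is singled out. Section 2.2 opens almost identically ("To determine the effect of dexamethasone, insert through Day 90 as measured by").

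**Related gaps.**
- Appendix I has the patient grade the current level of itching from 0 to 4, without saying that each eye gets its own score.
- Table 1 labels Visit 1 as Screening/Baseline and puts insertion at Visit 2, Day 0. Section 1.2.1 says "one eye will be randomized to receive the intracanalicular dexamethasone insert at the baseline visit (study eye"), where the visit can belong to the randomisation or to the insertion.
- There is no statistical section. No hypothesis, test, alpha, paired summary or success criterion appears anywhere.

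**The concern.** Someone who follows section 2.1 as written could report the before-after change in the insert eye as the primary result. Both eyes receive a steroid, so that change can be large and significant when insert and gel do not differ at all. It would not answer the question in section 1.2.

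An analyst who does compare the eyes still has four scales and several visits, and nothing says in advance which of them decides. For itching the comparison may not even be possible: if one score is recorded per patient, a between-eye result cannot be computed, and it cannot be recovered after the visits are over.

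**Working it through.** **Inputs from the documents.** 20 patients (40 eyes), one insert eye and one gel eye each; four primary scales; five visits. Visit 1 is the labelled Baseline, and section 5.2.1 lists the Day 0 gradings ahead of the insertion. Days 7, 30 and 90 are therefore the visits that clearly inform on treatment: 4 scales × 3 visits = 12 between-eye results.

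**What cannot be reproduced.** The sample size of 20 comes with no alpha, power, effect size, SD or correlation, so there is no design calculation to check.

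**Assumptions.** Two-sided 0.05, 20 complete pairs, effects in SD units, and the correlation ranges shown. The plan gives none of these.

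**1. Literal reading: test of change in the insert eye.** Suppose both eyes improve by the same d (in SDs of change). The one-sample t-test has 19 degrees of freedom, critical value 2.093 and noncentrality d√20.
- d = 0.5: 0.5 × 4.472 = 2.236, power 0.565.
- d = 0.8: 0.8 × 4.472 = 3.578, power 0.924.
- The paired insert-minus-gel difference has true mean zero, so its test rejects about 5% of the time. Simulation with between-eye correlation 0.3 to 0.8 gives 0.048 to 0.052.
- At d = 0.5 on all four scales, at least one insert-eye test is significant with probability 0.965, 0.859 or 0.751 for scale correlation 0, 0.5 or 0.8.

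**2. Between-eye reading: the error rate depends on the unstated rule.**
- Any one of 12 results may be claimed, no true effect, independent tests: 1 − 0.95^12 = 0.460. With visit/scale correlations of 0.3/0.2, 0.5/0.5, 0.7/0.7 and 0.8/0.9, simulation gives about 0.44, 0.37, 0.28 and 0.18.
- All four scales must succeed at one visit: 0.00003 to 0.018 when no scale has an effect, so under 2%. That figure is not the general bound. If three scales truly differ and one does not, a false claim needs only the fourth test to reject: simulated 2.7% to 2.8% with effects of 0.66 SD, and 4.2% to 5.0% with effects of 1.0 to 1.5 SD. The maximum is 5%.

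**3. Power cost of a rule.** Holm's first step over four scales uses 0.05/4 = 0.0125. With 20 pairs and 80% power (paired t-test):

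| Quantity | 0.05 | 0.0125 |
|---|---|---|
| Detectable paired difference (SD) | 0.66 | 0.81 |
| Power at 0.66 SD | 80% | 58% |
| Pairs for 80% power at 0.66 SD | 20 | 29 |

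If all four scales have a 0.66 SD effect, at least one succeeds under Holm with probability 0.969, 0.877 or 0.774 (scale correlation 0, 0.5, 0.8). All four succeed at 0.05 with probability 0.406, 0.548 or 0.653.

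**The case against.** The strongest reply is that the comparison is already there. The synopsis states it as the objective and labels a study eye and a control eye, and section 3.1 calls the trial randomised and fellow-eye, with the gel as comparator. In such a design a comparison of treatments is a comparison of eyes. This stands, and it narrows the point: what is missing is the step from that aim to the endpoint statistic.

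A reader might go further and infer that the sponsor intends a single-arm, insert-only analysis. The documents do not support that. Section 2.2 uses nearly the same lead-in for the patient's preferred therapy, measured by a questionnaire that compares medications, so the lead-in looks like loose general wording. The 56% to 92% therefore applies only if section 2.1 is followed to the letter.

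A reader might also take 46% as the trial's false-positive rate. No section plans a significance test, and mean changes at all visits are consistent with descriptive reporting in a 20-patient open-label study. The error rates show what an unstated rule could do, and predict nothing about what will be done.

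Finally, section 3.1 plans an abstract by May 2020, which might suggest that an early visit will decide the primary result. The abstract is described as preliminary, so that does not follow. The phrase about the period through Day 90 does not settle the visit either, since the bullets say all visits.

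**Conclusion.** The point holds in this form. The aim is insert versus gel, but the primary endpoint is written as the insert's change from Baseline and never as the difference between eyes. As worded it can be met without answering the study question. On the literal reading, with equal improvement of 0.5 to 0.8 SD in both eyes, that happens 56% to 92% of the time on one scale, against about 5% for the paired contrast.

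The lack of a deciding visit and of a rule for the four scales is a secondary part. Depending on the rule adopted, the chance of a false claim runs from under 2% (all four scales required, no effect on any; at most 5% in general) to about 18% to 46% (any one of 12 results). These figures rest on an assumed two-sided 0.05, 20 complete pairs and assumed effects and correlations.

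The gap on per-eye itching needs no such assumptions: without a score for each eye, one of the four primary scales cannot be compared between eyes.

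**What to change.** 1. In section 2.1 and the synopsis, restate the primary endpoint as the within-patient difference, insert eye minus gel eye, in change from Baseline. Analyse it as paired data, adjusted for the between-eye difference at Baseline.
2. Define Baseline in advance, either as Visit 1 (the schedule's label, but up to 30 days before insertion, which adds noise) or as the Day 0 grading made before insertion. Clarify the baseline-visit phrase in section 1.2.1 so that it agrees with Table 1.
3. Record itching separately for each eye in Appendix I and on the Case Report Form.
4. Report changes within each eye descriptively.
5. Name one deciding visit and one rule for the four scales in advance (one named scale, Holm, or all four required), or state that the four results are descriptive estimates with confidence intervals. The choice is the sponsor's.

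**Cost.** A protocol amendment with IRB review and a small form change for itching; no new visits or tests. Holm has the first-step power cost tabulated above, although the chance that at least one scale succeeds is still 77% to 97% if all four have a 0.66 SD effect. Requiring all four gives 41% to 65% power under the same effects. One named scale avoids the loss but leaves either allergy or dry eye outside the primary result.
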